Randomisation of stations to groups was carried out in accordance with the principles outlined in WORTH SOP24 Randomisation^[2]; specifically, randomisation was undertaken *after* paramedics in study stations had volunteered to participate (thus avoiding possible selection bias), and used centre and the number of eligible calls attended (based on data from 2009) as stratification variables. Clinical relevance is related to, but not determined by, the criterion of one event avoided (or incurred) in ten, which was the clinically significant effect size used in the sample size calculation. The calculated sample size for binary outcomes (whether an event occurred or not) is also adequate for a statistical assessment of the observed differences in times to the first event in the intervention and control group.

This analysis plan for SAFER 2 has been developed using appropriate CONSORT (www.consort-statement.org) statements and checklists, including those relating to cluster trials and patient-reported outcomes.

Section 2: TRIAL OBJECTIVES

The overall aim of this trial is to assess the benefits and costs to patients and the NHS of a complex intervention comprising education, clinical protocols and pathways enabling paramedics to assess older people who have fallen and refer them to community-based falls services when appropriate. Specific objectives are to:

- 1 Compare outcomes, processes and costs of care between intervention and control groups:
 - a patient outcomes: rate and pattern of subsequent emergency healthcare contacts or deaths, for any reason and for falls; health related quality of life (HRQoL); psychological status (especially fear of falling); and change in place of residence
 - b processes of care: pathway of care at index fall; subsequent healthcare contacts; ambulance service operational indicators and protocol compliance including clinical documentation
 - c costs of care: provided by NHS and personal social services; incurred by patients and carers in seeking care;
- 2 Estimate wider system effects of the introduction of the intervention on ambulance service performance and costs;
- 3 Understand how patients experience the new health technology;
- 4 Identify factors which facilitate or hinder the use of the intervention;
- 5 Inform the development of methods for falls research, especially outcome measures recommended for trials of interventions for older people who fall^[3]

Section 3: DATA COLLECTION & HANDLING

3.1 Data Sources & Collection

Our primary outcome is “further emergency healthcare contacts (999 call or Emergency Department (ED) attendance or hospital admission) or death for any reason and for falls per recruited faller, and time to first contact or death” for six months following the index call. This CRT does not approach participants at the point of treatment, because they may be in distress and unable to give informed consent, but seeks instead retrospective consent to follow up through routine medical records and by postal questionnaire. We planned to follow-up all our patients anonymously in order to achieve the primary outcome for our target sample size. In Wales, arrangements for this process are already in place through the existing SAIL (Secure Anonymised Information Linkage) Database, and our application for permission through the Information Governance Review Panel has been granted. We applied to the NIGB Ethics and Confidentiality Committee for permission to follow-up our patients anonymously through the Information Centre in England and permission has been granted for this process. Conditional to this permission, people who have clearly dissented to identifiable follow-up must be excluded from the study. For clarity, if a patient has at any time declined to be part of the study (either in returning a consent form or orally on the telephone) they will be removed from the study.

3.2 Sample Size and Statistical Power

We made the conservative estimate that trial patients have about 50% chance of making another emergency contact within six months; in the absence of intra-cluster correlation (ICC), a sample of 4190 evaluable participants yields 90% power, when using two-sided 5% significance level, of detecting a change in this chance from 50% to <45% or to >55%. The analogous outcome in the SAFER 1^[4] trial indicated an ICC of zero in clusters of participants seen by paramedics from the same ambulance station. To be conservative, we therefore allowed for an ICC of 0.002, and sought 251.6 (calculated from $0.998 \cdot 4190 / (25 - 0.002 \cdot 4190)$) participants per ambulance station, making a total sample size target of 6290.

However, actual recruitment is slightly lower, at 5939 participants, and we will lose approximately 1000 patients that decline to be part of the study. Furthermore, previous experience suggests that we shall also lose about 10% of the remaining patients from analysis because we shall not be able to match them with their routine electronic data on contacts with the NHS. Hence we expect the recruited sample of 5939 participants to yield only 4400 suitable for accurate information linkage. With an ICC of 0.002 and equal cluster sizes, this expected evaluable sample size corresponds to 3260 independent participants, which, in turn, equates to approximately 80% statistical power. In short, the cumulative loss in recruitment, and from dissenting and un-matched patients will reduce the statistical power of SAFER 2 from a conservative 90% to the traditional 80%, even allowing for more intra-cluster correlation than observed in the SAFER 1^[4] trial.

3.3 Missing Data

General Principles

As per WWORTH SOP28 Statistics^[5], we shall adopt a consistent approach to missing data relating to both effectiveness and cost-effectiveness except where individual outcome measures require some variation in that approach. We shall exclude participants without follow-up data, and, for each variable, summarise the frequency of missing data, which directly influences the sample size in, and hence the statistical power of, some analyses. If there is reason to suspect that data are not Missing Completely At Random (MCAR), the trial statistician and chief investigator will discuss the findings. If there is no reason to suspect that data are not MCAR, we shall use appropriate imputation methods to mitigate the problem of missing data.

Internal imputation of HRQoL data at a particular data collection point

None of the questionnaires (SF-12, derived SF-6D, or Modified Falls Efficacy Scale (mFES)^[6]) has an official algorithm for imputing individually missing answers. Some patients may have particular reasons for missing some of the questionnaire items, and it is unlikely that a plausible model for conditional Missing At Random can be established even on a case-by-case basis. Nevertheless, to minimise missing values and use available information, any such missing values within patient interviews will be completed by imputation^[7] within the reduced dataset of individual responses to questions in the three measures, using the regression or expectation maximization (EM) algorithms of the Missing Value Analysis module within SPSS. Scale scores will then be calculated according to the relevant instructions for the measure. The use of multiple imputation methods will be considered if the incidence of missing data is high.

External imputation of HRQoL data scores

If a participant is dead at the data collection point, the SF-6D score will be taken as zero. To avoid outliers, SF-12 and mFES scores will be taken as the minimum value observed for that measure in the relevant treatment group

Otherwise, missing summary scale and subscale scores will be imputed by regression from all available values of that score at other data points and the allocated treatment group. Further predictors (eg gender, age, current hospitalisation) may be included, unless they are already used as covariates in the main analysis

If any potential predictor other than study group has an F value of less than 1 (that is, it increases the standard error of the prediction) it will be removed from the list of predictors and the prediction recalculated.

Missing Health Economic data

Addressing the problem of missing data may involve employing Mean Imputation (that is, assigning a mean value to the respondents with missing data) or Regression Imputation (that is, using regression models to provide estimates of missing data from complete data, when the missing data is part of a multivariate data set). The usual method for dealing with censored data relating to costs will be to employ the weighted cost method with known cost histories^[8].

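### Missing SF-12 and mFES items are filled without treatment allocation and with no rule for scoring non-integer fills, giving a usually small bias towards no difference in the HRQoL and QALY comparisons

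*SAP*

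**What the plan says.** The item-level rule is in SAP section 3.3, under internal imputation of HRQoL data. Missing answers are filled "using the regression or expectation maximization (EM) algorithms of the Missing Value Analysis module within SPSS". Which of the two algorithms applies is left open. The information the model may draw on is restricted, because the filling is done "within the reduced dataset of individual responses to questions in the three measures". The next step is scoring: "Scale scores will then be calculated according to the relevant instructions for the measure". Nothing is said about rounding, bounding or mapping filled values to response levels. The same paragraph doubts its own premise, stating that "it is unlikely that a plausible model for conditional Missing At Random can be established even on a case-by-case basis", and ends with a fallback: "The use of multiple imputation methods will be considered if the incidence of missing data is high". It gives no threshold, model or variable list for that fallback.

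The score-level rule follows, under external imputation. Except where the participant has died, missing scale and subscale scores are "imputed by regression from all available values of that score at other data points and the allocated treatment group". Further predictors may be added, and weak ones are removed, but allocation is protected: the removal rule begins "If any potential predictor other than study group has an F value of less than 1".

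The scores concerned are secondary outcomes at one and six months (section 4.1, Objective 1a). SF-6D also supplies the QALYs (section 5.2).

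**The concern.** The plan has two imputation steps for the same measures and treats allocation in opposite ways. At score level it is always kept. At item level it is not in the dataset used, and no reason is given. An imputation model that omits a variable used in the later analysis weakens that variable's association with the filled values. Here that variable is the randomised comparison itself, so the bias runs towards no difference.

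There is a second, separate gap. Regression and EM of this kind predict on a continuous scale, whereas questionnaire answers are discrete. An analyst following the plan would have to decide, with the data in hand, what to do with a filled answer of 2.37, say, before applying the scoring instructions.

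At stake are the between-arm estimates for SF-12, SF-6D and mFES, and through SF-6D the cost per QALY.

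**Working it through.** The plan gives no figure on this point: no rate of missing items, no inter-item correlation and no item count. Everything below rests on assumed inputs, so ranges are shown.

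**1. What a filled item keeps.** Assume equal correlation rho between items, an arm effect acting through one common factor, k other items observed and no allocation term. The share of the arm difference that survives in a filled item is

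r = k·rho / (1 + (k − 1)·rho).

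With k = 11 (assumed: 12 items, one missing):
- rho = 0.2: 2.2 / 3.0 = 0.733
- rho = 0.6: 6.6 / 7.0 = 0.943

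**2. What the score loses.** If a fraction m of items is missing and the score weights items equally, the score keeps (1 − m) + m·r of the difference and loses m·(1 − r). At m = 0.10:
- rho = 0.2: 0.10 × 0.267 = 2.7%
- rho = 0.6: 0.10 × 0.057 = 0.6%

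At rho = 0.36, r is 1.80/2.44 = 0.738 with 5 other items and 3.96/4.60 = 0.861 with 11. The losses at m = 0.10 are 2.6% and 1.4%.

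**3. Simulation check.** Normal-theory EM was run on 12 five-level items, 3000 patients and 4 replicates. Items were missing completely at random and the latent effect was 0.3 SD. Here rho is the correlation before responses are cut into levels. Entries are the share of the full-data arm difference kept, without / with allocation in the EM model.

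| Effect | rho | 5% missing | 10% missing | 20% missing |
|---|---|---|---|---|
| Common to all items | 0.3 | 0.981 / 0.991 | 0.967 / 0.987 | 0.941 / 0.986 |
| Common to all items | 0.5 | 0.998 / 1.003 | 0.987 / 0.997 | 0.982 / 1.005 |
| On 3 of 12 items, measured on those 3 | 0.3 | 0.949 / 0.990 | 0.917 / 0.996 | 0.845 / 1.010 |
| On 3 of 12 items, measured on those 3 | 0.5 | 0.956 / 0.999 | 0.942 / 1.026 | 0.860 / 1.004 |

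With allocation, 0.99 to 1.03 is kept, which is no attenuation beyond simulation noise. Without it, 0.94 to 1.00 is kept for a common effect and 0.85 to 0.96 for an item-specific one. The formula agrees: at rho = 0.3 and 10% missing it gives 0.10 × (1 − 0.825) = 1.75%, against a simulated gap of 0.987 − 0.967 = 0.020.

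**4. Fractional values.** About 98% of EM-filled values lay more than 0.01 from a whole response level. That is what a continuous prediction would give, since a window of ±0.01 covers 2% of each unit. Practically none fell outside the 1 to 5 range. Adding allocation does not change the fractional character of the values.

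**The case against.** The strongest reply is that a patient's other answers already carry most of the arm effect, so omitting allocation costs little. That stands, and it sets the size of the finding.

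It can also be said that filling a skipped answer and imputing a wholly missing score are different tasks, and that section 3.3 lets the approach vary where an individual measure requires it. But no such requirement is stated, and nothing about a skipped item calls for leaving allocation out.

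The plan does mention multiple imputation, and heavy missingness, where the bias would matter most, is when it would be considered. That is fair, but the sentence commits to nothing. Multiple imputation in its standard form also rests on the missing-at-random assumption that the plan doubts. So does the regression or EM step it would replace, and neither repairs data missing for unrecorded reasons.

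Three stronger readings are tempting but not supported:
- *That arm differences shrink by 10% to 30%.* For a single item whose effect no other item shares, a difference of 0.20 falls to about 0.18, 0.16 or 0.14 at 10%, 20% or 30% missing. That is a worst case for one item; the plan analyses scale scores.
- *That filled answers collapse to the commonest category.* In a simulated yes/no item with 25% answering yes, rounding linear predictions leaves about 6% yes. The plan states no rounding, and before rounding the mean prediction is correct.
- *That the filled values cannot be scored.* The SAP does not describe response formats or scoring algorithms. If a measure sums or averages its items, fractional values can be used. What the text supports is that no rule is given.

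**Conclusion.** The point holds in a limited form. As written, the item-level step leaves out allocation while the score-level step for the same measures always keeps it. The resulting bias is towards no arm difference in SF-12, SF-6D, QALYs and mFES. For a common effect it is about 0.6% to 2.7% of a score difference at 10% missing items, assuming 11 other observed items, correlations of 0.2 to 0.6 and equal item weights. It can reach about 15% on the affected items when the effect is confined to a few and 20% of items are missing. Since the plan gives neither the missing rate nor the correlations, whether it matters in this trial is not shown.

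The lack of a rule for non-integer fills is a real gap in specification, not a demonstrated bias. The emergency-contact and death outcomes are untouched. This is a modest defect, worth correcting because the correction is nearly free and the plan's own next step already applies its main part.

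**What to change.** In SAP section 3.3, internal imputation:

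- Add allocated group to the item-level imputation model and exempt it from removal, matching the score-level rule. This alone removes the attenuation.
- Replace the choice between regression and EM with one named method that returns real response levels, such as predictive mean matching or ordinal models within multiple imputation. Score each completed dataset by the measure's instructions and combine the estimates. If a single fill is kept, state how filled values are mapped to response levels or passed to scoring.
- Replace the open-ended mention of multiple imputation with a firm statement of when it applies and which variables it uses.

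The cost is a change of SAP wording and the handling of several imputed datasets instead of one, in standard software. No new data are needed.

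### The imputation rules for questionnaire and cost outcomes bar the analysis covariates, default to single imputation, and rest on a reversed MCAR condition that the specific rules do not follow

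*SAP*

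**What the plan says.** SAP section 3.3 sets rules at several levels.

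- **General principle.** "If there is no reason to suspect that data are not MCAR, we shall use appropriate imputation methods". If MCAR is doubted, the statistician and the chief investigator confer, and no method is named. Participants with no follow-up data are excluded.
- **Missing questionnaire items.** The section says that a credible MAR model is unlikely, then imputes all the same with the regression or EM routine in SPSS. It adds: "The use of multiple imputation methods will be considered if the incidence of missing data is high". No threshold is given.
- **Missing scale scores.** Apart from deaths, which receive fixed values, scores are imputed by regression on the same score at other times and on allocated group. Then: "Further predictors (eg gender, age, current hospitalisation) may be included, unless they are already used as covariates in the main analysis".
- **Costs.** The options are "Mean Imputation (that is, assigning a mean value to the respondents with missing data") or regression imputation. The SAP does not say whether the mean is taken within arm or overall.

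Section 3.4 imputes data missing through withdrawal wherever that can be done. Section 5.1 names age and gender among the candidate covariates and extends the principles of the primary analysis to quantitative secondary outcomes. Section 5.2 plans bootstrapping for acceptability curves and confidence intervals.

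**The concern.** There are three separate defects.

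**Barred covariates.** An imputation model that leaves out an analysis covariate assumes that, given group and the other score, the covariate has no association with the missing score. If it does have one, the imputed records lack it, and the covariate's coefficient in the analysis is pulled towards zero. The clause removes exactly the variables that ought to be in, and its own examples include age and gender.

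**Single values.** A score filled in once by its predicted value carries no residual scatter and no uncertainty about the prediction. If the completed data are then analysed in the usual way, standard errors are too small.

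**Reversed condition.** Under MCAR, complete cases are already unbiased, so imputation can gain only precision. Imputation is needed to reduce bias when missingness depends on observed data, and for that case the general principle fixes nothing. The item, score and withdrawal rules carry no MCAR condition at all, so two analysts could both follow the plan and do different things.

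At stake are the SF-12, SF-6D and mFES comparisons, the QALYs and the costs, which together carry the cost-effectiveness result.

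**Working it through.** **The plan's own figures.** The SAP gives no missing fraction or correlation for questionnaire or cost data. Its only related arithmetic concerns the primary outcome, and it reproduces: 0.998 × 4190 / (25 − 0.002 × 4190) = 251.6 per station, 6290 in total; 4400/25 = 176 per station, design effect 1 + 175 × 0.002 = 1.35, and 4400/1.35 = 3259 against the stated 3260. None of this bears on imputation. The inputs below are assumptions unless a section is named.

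**1. Single regression imputation.** Let f be the missing fraction (MCAR) and ρ = 0.6 the correlation between time points, so ρ² = 0.36; outcome variance 1, n per arm, no true effect. Impute from group and the other score, then compare arm means.

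- Variance reported, per arm: (1 − f + fρ²)/n
- True variance, per arm: (ρ² + (1 − ρ²)/(1 − f))/n
- k = √(reported/true); type I error = 2[1 − Φ(1.96k)]

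| f | reported × n | true × n | k | type I error |
|---|---|---|---|---|
| 10% | 0.936 | 1.071 | 0.935 | 6.7% |
| 20% | 0.872 | 1.160 | 0.867 | 8.9% |
| 40% | 0.744 | 1.427 | 0.722 | 15.7% |

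Simulation with n = 1000 in total agrees: about 6%, 9% and 15%.

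**2. Mean imputation of costs.** With an arm-specific mean, the reported variance is (1 − f)/n and the true variance 1/[n(1 − f)], so k = 1 − f. Type I error is 2[1 − Φ(1.96 × 0.8)] = 11.7% at 20% missing and 2[1 − Φ(1.96 × 0.6)] = 24.0% at 40%. With one overall mean, reported and true variance are both (1 − f)/n, so k = 1 and type I error stays near 5% (4.9% and 5.1% in simulation). A true difference is then multiplied by 1 − f, that is by 0.8 or 0.6.

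**3. Barring the covariate.** Simulation: 1500 participants, 1000 runs per setting, no treatment effect, two time points, a covariate with coefficient 0.40 that also drives missingness, residual correlation 0.3 to 0.6, nominal missing 10%, 30% and 50%.

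| Method | Covariate coefficient (10 / 30 / 50%) | Coverage of 95% interval for treatment (10 / 30 / 50%) |
|---|---|---|
| As written: single, covariate barred | 0.36–0.375 / 0.30–0.34 / 0.26–0.32 | 92% / 84–89% / 72–80% |
| Single, covariate included | 0.40 throughout | 72–93% over all settings |
| Multiple (15 imputations), covariate included | 0.40 throughout | 94–96% over all settings |

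So the clause damages the covariate coefficient, and single imputation damages the interval; each needs its own repair. In a second setting, with an age coefficient of -0.60 and about 39–40% missing, the coefficient fell to about -0.45 (runs with differing inputs gave -0.44 to -0.50) and was restored once age was included.

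**4. Treatment effect.** When missingness depended on the covariate alone, the treatment estimate was unbiased. When the dependence on age differed by arm (about 38–39% missing), a null effect became 0.05 to 0.07 in absolute value, against 0.001 to 0.005 with age in the imputation model. The sign follows the direction of the dependence.

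**The case against.** Several stronger readings are tempting, and the SAP does not support them.

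- **That data are imputed only when MCAR is not doubted.** The item, score and withdrawal rules impute unconditionally, and section 3.3 allows individual measures to depart from the general approach. The defect is a reversed principle in conflict with its own specific rules. That principle also follows a standard operating procedure that is not shown, so what would come after the discussion cannot be judged.
- **That the clause biases the treatment effect in general.** It does so only if missingness depends on the covariate differently by arm. Nothing in the SAP shows that this will happen, although postal questionnaires and retrospective consent (section 3.1) leave it open. Age and gender are also only candidate covariates, dropped if F is below 1.
- **That mean imputation must inflate type I error.** It does so only with an arm-specific mean, which the SAP does not specify. The cost wording is also permissive.
- **That single imputation is fixed without exception.** Multiple imputation is to be considered, though with no threshold and only under the item-level heading. That completed values are analysed as if observed is inferred from the absence of any variance correction.
- **That the acceptability curves are bound to be too optimistic.** This depends on whether imputation is repeated inside each bootstrap sample, which the SAP does not state.

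Two limits also stand. The effect is confined to secondary outcomes. And because people without follow-up are excluded, score imputation may on one reading reach only those who returned one of two questionnaires, which makes a 40% imputed share less likely.

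None of this rescues the exclusion clause or single imputation as the default.

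**Conclusion.** The point holds in this limited form: followed as written, the section 3.3 rules give wrong results for the questionnaire and cost outcomes. The clause is wrong whenever an analysis covariate predicts the score beyond group and the other time point. The single-imputation default understates uncertainty by an amount that grows with the missing share: modest at 10%, where type I error is about 6–7%, and serious at 40%, where it is about 15–16%. The MCAR rule is reversed and inconsistent with its neighbours. The sizes rest on assumed missing fractions, correlations and covariate strengths. The direction of the standard-error fault does not, provided that completed data are analysed without correction; an overall mean for costs is the exception, since it dilutes the difference instead. The primary outcome, taken from linked routine records, is untouched. The change should be made before these outcomes are analysed.

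**What to change.** In section 3.3:

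1. Delete the clause that keeps main-analysis covariates out of the score imputation model, and delete the mean-imputation option for costs.
2. Make multiple imputation under MAR the standard for questionnaire scores and costs. The model should include group, station or centre, every analysis covariate, the other time point and, where it can be linked, the primary outcome. Section 6.2 already plans to compare questionnaire responders and non-responders on the primary outcomes.
3. Combine results by Rubin's rules, or repeat the imputation within each bootstrap sample for the acceptability curves, and state which.
4. Remove the MCAR condition, so that the general principle agrees with the item, score and withdrawal rules.

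A delta-shift sensitivity analysis for MNAR would be a useful option but is not needed to correct the error. The cost is a revision of the SAP text, modest programming in standard software, and wider intervals.
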